1. AMENDEMNT HISTORY

Amendment	Protocol	Date	Author(s) of changes	Details of Changes made
No.	Version	issued		
	No.			

4

2. SUMMARY

This is an observational retrospective multicentre study registry aiming at evaluating the outcomes of patients affected by type A acute aortic dissection (TAAD) undergoing surgery.

Understanding the patient's conditions and treatment strategies which are associated with postoperative outcomes is essential for an appropriate management of acute TAAD. The analysis of this large multicentre registry will allow more conclusive results on the prognostic importance of critical preoperative conditions and the value of different treatment strategies to reduce the risk of early adverse events after surgery for acute TAAD. This registry will provide insights into the long-term durability of surgery for TAAD.

3. SYNOPSIS

Title of Study	Transatlantic Registry of Type A Aortic Dissection (TARTAAD)		
Sponsor	University Hospital of Helsinki (Finland)		
Study	Primary Hypothesis: understanding the patient's conditions and		
Hypothesis	treatment strategies which are associated with postoperative		
	outcomes is essential for an appropriate management of acute TAAD		
Study	Primary objective: to identify the predictors influencing early and late mortality		
Objectives	in TAAD patients undergoing open heart surgery		
	• Secondary objectives: to elucidate and identify predictors of: 1) re-		
	exploration for bleeding; 2) cerebrovascular accident 3) surgical site infection;		
	4) blood transfusion; 5) acute kidney injury; 6) length of intensive care unit		
	(ICU) stay; 7) length of hospital stay and 8)		
	reoperation after hospital discharge; 8) late survival; 9) rate of late re-intervention.		
Study Design	Retrospective observational cohort study registry		
Planned Sample	This study will use data from 32 high-volume aortic centers.		
Size	It is anticipated that the final database will approximately contain clinical		
Culain at	details for more than 10000 patients.		
Subject	Inclusion criteria:		
Selection Criteria	• Type A aortic dissection or intramural hematoma involving the aortic		
Criteria	root/ascending aorta; • Patients aged > 18 years: • Symptoms started within 7 days from surgery; • Primary surgical repair of acute type A aortic dissection;		
	Any other major cardiac surgical procedure		
	concomitant with surgery for type A aortic dissection		
Intervention	This is a non-interventional study		
Study period	1 January 2010 – 31 December 2024		
Follow-up/End-	31 December 2025		
study			
Primary	Mortality rate during the index hospital stay until last follow-up control		
Outcomes	Cumulative incidence of reoperation on the aorta during the index hospital		
	stay until last follow-up control (any surgical and endovascular procedure on		
	any segment of the aorta for aortic dissection or its		
0	related complication)		
Secondary	1) Incidence of stroke; 2) Incidence of acute kidney injury; 3) Incidence of		
Outcomes	surgical site infection; 4) Incidence of reoperation for bleeding; 5) Incidence		
	and amount of blood transfusion; 6) Length of stay in the intensive care unit; 7) Incidence of global brain ischemia; 8) Incidence of paraplegia/paraparesis; 8)		
	late survival; 9) rate of late re-intervention		
	late salvival, syrate of late to intervention		
Statistical	Continuous variables will be reported as mean and standard deviation or		
Considerations	median and interquartile range as needed. Dichotomous and nominal variables		
	will be reported as counts and percentages. Univariate analysis will be		
	performed using the Mann-Whitney U test, Student's t-test, Kruskall-Wallis test,		
	Wilcoxon test, Fisher exact test, Chi-square test, Kaplan-Meier test.		
	Multivariable analyses will be performed using logistic, classification tree,		
	linear and ordinal regression methods. A Bayesian hierarchical approach will		
	be used in case of significant between center variability.		

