6.2. Objectives

The primary objective of this retrospective study is to identify the predictors influencing the mortality rate during the index hospital stay until last follow-up control, and the cumulative incidence of reoperation on the aorta during the index hospital stay until last follow-up control. Secondary objectives include: 1) incidence of stroke; 2) incidence of acute kidney injury; 3) incidence of surgical site infection; 4) incidence of reoperation for bleeding; 5) incidence and amount of blood transfusion; 6) length of stay in the intensive care unit; 7) incidence of global brain ischemia; 8) incidence of paraplegia/paraparesis

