7.5. Schedule

Only TAAD patients undergoing open heart surgery between 1 January 2010 and 31 December 2024 will be retrospectively retrieved and enrolled in the study. Deadline for submission of data is set up for 31 December 2021.

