8.2. Sample Size Calculation

The impact of total aortic arch repair compared to more limited aortic resection on the early and late outcomes will be one of the main topics of research from this registry. Therefore, in the light of the expected limited frequency of this surgical strategy, we performed a sample size analysis considering the extent of distal aortic resection. Despite the limitation of a pooled analysis which did not take in to account the cumulative incidences from competing risk analysis and the segment of repeat operation, Poon et al. (24) estimated a pooled hazard ratio on 0.73 (95%CI 0.56-1.18) of freedom from any late aortic reoperation for total arch replacement. Based on this hazard ratio, a sample size of 163 patients per study groups would be enough to reject the null hypothesis (alpha 0.05, power 0.80). Pan et al. (25) reported a freedom from distal reoperation after ascending aortic resection at 8 years of 95.3% which was not statistically different from that of hemiarch or total aortic arch repair (92.4%, p=0.22). For the sample size calculation of a non-inferiority trial, we assumed a freedom rate from distal aortic reoperation of 95% and we considered that a difference in the reoperation rate as large as 10% in favor of a total aortic arch repair still allow the less extensive repair to be non-inferior (delta=0.1, power 0.90, one-sided confidence 97.5%), the required sample size would be 100 patients per each group. We assume that about 5% of patients have undergone total arch repair in this collaborative registry and therefore a study population of 4000 patients would be enough to investigate the impact of total aortic arch repair in preventing late aortic reoperation in patients with acute TAAD.

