Logistic and linear regression analyses will be employed to identify independent risk factors for early adverse events with and without a stepwise approach. For the purpose of developing a risk scoring method from this registry, the study cohort will be randomly divided into two datasets, i.e. the derivation data set (75.0% of patients) and the validation data set (25.0% of patients). Univariate analysis will be performed on all candidate covariates of the derivation dataset to identify predictors of in-hospital mortality. Multiple logistic regression analysis will be then performed using the derivation dataset. A stepwise procedure with a bootstrap approach will be used, and 100 samples will be extracted with a size of 70% of the derivation dataset. A stepwise procedure will be applied to each sample (probability to stay = 0.05; probability to entry = 0.1). Variables selected in at least 50% of the stepwise procedures will be included in the regression model. Additional covariates were selected using a forward selection comparing the Akaike information criterion for the models with and without each covariate. The model with the lowest Akaike information criterion will be selected for each forward step, until the inclusion of a new covariate determined an increase in the Akaike information criterion value. The model will be tested in the validation data set for calibration, using the Hosmer-Lemeshow test, and for discrimination using the receiver-operating characteristic curve analysis. A comparison of the predictive ability of the new score with the current risk scoring methods for prediction of in-hospital mortality will be performed in the overall dataset as well as in the validation dataset using the DeLong test. The improvement of discrimination of the new score will be estimated by calculating the net reclassification index and the integrated discrimination improvement.

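### The listed multivariable methods include no time-to-event or competing-risk model, although both primary outcomes run to last follow-up

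*Protocol*

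**What the plan says.** **Outcomes.** The synopsis gives the first primary outcome as "Mortality rate during the index hospital stay until last follow-up control"; the second is aortic reoperation over the same span. Section 6.2 sets as the primary objective a search for "the predictors influencing the mortality rate during the index hospital stay until last follow-up control, and the cumulative incidence of reoperation on the aorta", and the synopsis words it as "Primary objective: to identify the predictors influencing early and late mortality". A multivariable analysis of the late outcomes is therefore part of the primary objective.

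**Follow-up.** Section 7.5 says "Only TAAD patients undergoing open heart surgery between 1 January 2010 and 31 December 2024 will be retrospectively retrieved". Section 12.5 closes follow-up for everyone on 31 December 2025. Section 7.7 defines the last follow-up date as the date last known alive or the date of death.

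**Methods.** The synopsis states: "Multivariable analyses will be performed using logistic, classification tree", then linear and ordinal regression, with a Bayesian hierarchical approach for between-centre variability. Kaplan-Meier appears once, in the list of univariate tests. Section 8.3 (Statistical Analysis) states: "Logistic and linear regression analyses will be employed to identify independent risk factors for early adverse events with and without a stepwise approach". It also plans a risk score for in-hospital mortality, centre and surgeon comparisons of early outcomes, propensity matching of treatment strategies, and use of the propensity score in regression models whose type is not given.

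**Sample size.** Section 8.2 starts from a pooled hazard ratio of 0.73 for late reoperation. It remarks that the pooled analysis behind it "did not take in to account the cumulative incidences from competing risk analysis". That is the only mention of competing risk in the text shown.

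**The concern.** The protocol names its multivariable methods, and those named do not fit the late part of either primary outcome. Logistic regression or a classification tree on death or reoperation by last follow-up treats a patient observed for 1 year and one observed for 16 years as equally informative. The result then depends on when patients were operated on as well as on their risk. For reoperation, death is also a competing event: a patient who has died cannot be reoperated.

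At stake are the late-mortality predictors and the comparison of limited with total arch repair, which Section 8.2 calls one of the registry's main topics. A factor more common in recent years could look protective only because its carriers were watched for less time.

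**Working it through.** **1. Follow-up range.** From 1 January 2010 to 31 December 2025 is 16.0 years; from 31 December 2024 to 31 December 2025 is 1.0 year. These are potential times; death and loss to follow-up shorten them.

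**2. Scale of the plan's own sample size.** With HR 0.73, two-sided alpha 0.05, power 0.80 and equal groups:
- Schoenfeld: 4 × (1.960 + 0.842)² / (ln 0.73)² = 31.4 / 0.0990 = 317 events.
- Freedman: (1.960 + 0.842)² × (1.73 / 0.27)² = 323 events.

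The stated 163 per group is 326 in total, within 3% of both. The figure thus reproduces from hazard-ratio formulas, and no multivariable method named in the protocol estimates a hazard ratio. (These formulas count events, whereas the protocol labels the number as patients; that is a separate matter.)

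**3. Crude proportions by operation date.** Early death is 17%, the 30-day figure in Section 5.1. Assumed, not in the documents: late death h_d = 4%/year and reoperation h_r = 1%/year, both constant.
- Dead by time T: 1 − 0.83·exp(−h_d·T). At 1 year this is 20%; at 16 years, 56%.
- Reoperated by T: 0.83·h_r/(h_r + h_d)·[1 − exp(−(h_r + h_d)·T)]. At 1 year this is 0.8%; at 16 years, 9.1%.

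Two patients with identical risk thus have very different chances of being recorded as events.

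**4. Spurious odds ratio for a technique with no effect.** Mean total arch use is 5% (Section 8.2). A linear change in use over 2010–2024 is assumed. Mid-year operations give T = 15.5 down to 1.5 years. The probabilities in step 3 are averaged over the operation years of each group.

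| Total arch use | Mean potential follow-up, total arch / limited (years) | Reoperated, total arch / limited | Crude OR |
|---|---|---|---|
| 1 to 9% | 6.4 / 8.6 | 4.3% / 5.6% | 0.77 |
| 3 to 7% | 7.4 / 8.6 | 4.9% / 5.5% | 0.88 |
| 4 to 6% | 8.0 / 8.5 | 5.2% / 5.5% | 0.94 |
| constant 5% | 8.5 / 8.5 | 5.5% / 5.5% | 1.00 |

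Varying h_r from 0.6 to 1.5%/year leaves these values almost unchanged. For death, the two steeper trends give 0.80 and 0.89. All are before any adjustment for operation year.

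**5. Kaplan-Meier, if used for reoperation.** With deaths censored, 1 − KM = 1 − exp(−h_r·t). At 8 years with h_r = 1%/year this is 7.7%.
- h_d = 3%/year: true incidence among early survivors is 6.8%, ratio 1.12; among all operated, 5.7%, ratio 1.35.
- h_d = 5%/year: 6.4%, ratio 1.21; and 5.3%, ratio 1.46.

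The step from the first ratio to the second is the factor 1/0.83 = 1.20 from early deaths. Late death alone accounts for 1.12 to 1.21.

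**The case against.** The best defence is that nothing in the protocol assigns logistic regression to late death or late reoperation. Section 8.3 ties logistic and linear regression to early events, in-hospital mortality and early centre comparisons, where logistic regression suits the binary outcomes. The late model might then be left to an analysis plan that is not shown. This has force against any claim that a wrong late analysis is definitely planned. It does not clear the synopsis, which states what the multivariable methods will be without limiting them to early outcomes, beside primary outcomes that need something else.

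Four stronger readings are tempting, and the documents do not support them:
- **Section 8.3 covers only early events.** It does not say so: the propensity matching and the propensity-adjusted regressions carry no such limit. If operation year is among the baseline variables in the propensity model, much of the imbalance in step 4 would be removed from matched comparisons. The protocol does not say whether it is.
- **Reoperation incidence will be overstated.** Kaplan-Meier is never tied to reoperation. It suits all-cause death, and the reoperation outcome is worded as "the cumulative incidence of reoperation on the aorta during the index hospital stay until last follow-up control". Step 5 is therefore conditional.
- **Technique changed over calendar time.** The protocol gives only an overall share of about 5% for total arch repair.
- **Linear regression will score early deaths as short intensive-care stays.** No passage assigns linear regression to that outcome, and the 17% is 30-day mortality from another source, not death in intensive care.

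**Conclusion.** The point holds as a mismatch between the stated multivariable methods and the late primary outcomes. It rests on the protocol's own text: outcomes to last follow-up, potential follow-up of 1 to 16 years, sizing on a hazard ratio, and no named time-to-event or competing-risk regression. It does not depend on any trend in technique.

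The size of the harm does depend on assumptions. A spurious crude odds ratio for reoperation ranges from 0.77 under a steep assumed trend to 1.00 under none, and adjustment for operation year would reduce it. Overstatement of reoperation by 1.12 to 1.21 fold at 8 years from late death, or 1.35 to 1.46 fold with early deaths counted, arises only if Kaplan-Meier is used for that outcome, and rests on an assumed late mortality of 3 to 5%/year. These figures show what the listed methods could do if applied to the late outcomes; they do not predict the registry's results.

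**What to change.** In the synopsis and Section 8.3 (Statistical Analysis), assign a method to each primary outcome:
- **All-cause death:** Cox regression from the date of surgery, censored at the date last known alive, allowing for centre.
- **Aortic reoperation:** Aalen-Johansen cumulative incidence, with one competing-risk regression in which death competes, either cause-specific Cox or Fine-Gray.
- **Logistic regression:** restrict it to in-hospital or other early binary events.

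The cost is a change of wording and a little more analysis work, with one condition. Section 7.7 lists the aortic segments treated and the indication for each reoperation, but does not name its date. The date must be confirmed as a collected variable. If it is not, it has to be added to the dataset and obtained from the centres, which is more than a wording change.

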4. ABBREVIATIONS

CKD-EPI Chronic Kidney Disease Epidemiology Collaboration

E-CABG European Coronary Artery Bypass Grafting registry

EKFC European Kidney Function Consortium

ERTAAD European Registry of Type A Aortic Dissection

KDIGO Kidney Disease: Improving Global Outcomes

RBC Red Blood Cell

TAAD Type A Aortic Dissection

-- 7

5. BACKGROUND AND RATIONALE

5.1. Background

Acute Stanford type A aortic dissection (TAAD) is a life-threatening condition. Surgery is usually performed as a salvage procedure and is associated with increased postoperative early mortality and morbidity (1). Although early mortality has declined during the last years (2), the recent The Nordic Consortium for Acute Type A Aortic Dissection registry including 1189 patients operated from 2005 to 2015 in 8 centers showed that 30-day mortality after surgery for acute TAAD was 18% (3). The multicentre, prospective German Registry for Acute Aortic Dissection Type A including 2137 TAAD patients operated from 2006 and 2010 documented a 30-day mortality of 16.9% (4). A more recent analysis of the Society of Thoracic Surgeon database including 7353 patients operated from 2014 and 2017 for acute TAAD reported a 30-day mortality of 17% (5). Furthermore, surgery for TAAD is often complicated by major adverse events such as stroke (5) and acute kidney failure (6), which may have a significant impact on late survival. In this scenario of significant postoperative mortality and morbidity, surgeon faces the controversial issue of the extent of surgical repair for acute TAAD by avoiding a major surgical repair with its possible increased risk of early adverse event. At the same time, the surgeon would need to decide on whether to resect aortic segments which may expose the patient to the risk of late complications at the level of the aortic root (7) as well as of the aortic arch or distal to it (8). Understanding the balance between the patient's conditions which may not allow extensive procedure and those treatment strategies which may limit the risk of late adverse events in patients who remain alive long after the surgery is essential for an appropriate management of TAAD. We aim to create the present multicenter European registry of surgery for acute TAAD (ERTAAD) to evaluate the contemporary early outcomes and late durability of different surgical strategies for acute TAAD in a large study population within a long follow-up period.

5.2. Rationale of the Study

The analysis of this multicentre registry will allow more conclusive results on the prognostic importance of critical preoperative conditions and the value of different treatment strategies to reduce the risk of early adverse events after surgery for acute TAAD. This registry will provide insights into the long-term durability of surgery for TAAD.

6. AIMS AND OBJECTIVES

6.1. Primary hypothesis

Understanding the patient's conditions and treatment strategies which are associated with postoperative outcomes is essential for an appropriate management of acute TAAD.

6.2. Objectives

The primary objective of this retrospective study is to identify the predictors influencing the mortality rate during the index hospital stay until last follow-up control, and the cumulative incidence of reoperation on the aorta during the index hospital stay until last follow-up control. Secondary objectives include: 1) incidence of stroke; 2) incidence of acute kidney injury; 3) incidence of surgical site infection; 4) incidence of reoperation for bleeding; 5) incidence and amount of blood transfusion; 6) length of stay in the intensive care unit; 7) incidence of global brain ischemia; 8) incidence of paraplegia/paraparesis

7. STUDY DESIGN AND METHODS

7.1. Study Design

The ERTAAD is an observational registry, and its data will be retrospectively collected from 20 centers of cardiac surgery of university hospitals located in eight European countries (Belgium, Czech Republic, Finland, France, Germany, Italy, Nederland, Spain, United Kingdom and USA). Below the list and location of participating centres:

	Participating hospitals	Contact persons	E-mail addresses
1	Heart and Lung Center, Helsinki University Hospital, University of Helsinki, Helsinki, Finland	[name] [name] [name] [name] [name]	[contact]; [contact]; [contact]; [contact]
2	Department of Cardiac Surgery, John Radcliffe Hospital, Oxford University Hospitals NHS Foundation Trust, Oxford, UK	[name] [name]	[contact] [contact]
3	Department of Cardiovascular Surgery University Heart and Vascular Center Hamburg, Hamburg, Germany	[name]	[contact]
4	Erasmus Medical Center, Rotterdam, Holland	[name]	[contact]
5	Department of Cardiothoracic Surgery, University Hospital Cologne, Cologne, Germany	[name] [name] [name]	[contact] [contact] [contact]
6	Department of Cardiovascular Surgery, Glenfield Hospital, Leicester, UK	[name] [name]	[contact] [contact]
7	Department of Cardiovascular Surgery, University of Liverpool, Liverpool, UK	[name] [name] [name]	[contact]; [contact]; [contact]
8	Department of Cardiovascular and Thoracic Surgery, Cabrol University Hospital, Reims, France	[name]	[contact]
9	Department of Cardiac Surgery, University of Dijon, Dijon, France	[name] [name]	[contact] [contact]
10	Department of Cardiac Surgery, Varese Hospital, Varese, Italy	[name]	[contact]

11	Department of Cardiac Surgery, Martin Luther University Halle- Wittenberg, Halle, Germany	[name]	[contact]
12	Department of Cardiac Surgery, LMU University Hospital, Ludwig Maximilian University, Munich, Germany	[name]	[contact] [contact]
13	Department of Cardiovascular Surgery, Hospital Clínic de Barcelona, University of Barcelona, Spain	[name] [name]	[contact] [contact]
14	Department of Cardiac Surgery, Charles University and University Hospital Kralovske Vinohrady, Prague, Czech Republic	[name] [name]	[contact] [contact]

7.2. Inclusion criteria

- TAAD or intramural hematoma involving the aortic root/ascending aorta
- Patients aged > 18 years
- Symptoms started within 7 days from surgery
- Primary surgical repair of acute TAAD
- Any other major cardiac surgical procedure concomitant with surgery for TAAD

7.3. Exclusion criteria

- Patients aged < 18 years
- Onset of symptoms > 7 days from surgery
- Prior procedure for TAAD
- Retrograde TAAD (with primary tear located in descending aorta)
- Concomitant endocarditis
- TAAD secondary to blunt or penetrating chest trauma

